5.1.2 Exclusion criteria

- Diagnosis other than osteosarcoma
- ^{99m}Tc-MDP bone scan with no significant uptake (i.e. “nothing” for a bone-seeking isotope to target/ i.e. indicator lesion that would be expected to have the bone-seeking targeted uptake of 223-radium dichloride)
- Other malignancy treated within the last 3 years (except non-melanoma skin cancer or low-grade superficial bladder cancer)
- Any other serious illness or medical condition, such as but not limited to:
 - Any active infection \geq National Cancer Institute Common Terminology Criteria for Adverse Events (NCI-CTCAE) version 4.03 Grade 2
 - Cardiac failure New York Heart Association (NYHA) III or IV
 - Fecal incontinence (this is because of Ra-223 elimination in feces)
- Women who are pregnant or breast-feeding.
- Inability to comply with the protocol and/or not willing or not available for follow-up assessments.

- Any condition which, in the investigator's opinion, makes the subject unsuitable for trial participation.
- Concurrent anti-cancer therapy (chemotherapy, radiation therapy, surgery, immunotherapy, biologic therapy, or tumor embolization)
- Patients on oxygen

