5.2 Withdrawal of subjects from study

5.2.1 Withdrawal

Subjects **must be withdrawn from the trial** (treatment and procedures) for the following reasons:

- Subject withdraws consent from study treatment and study procedures. A subject must be removed from the trial at his/her own request or at the request of his/her legally acceptable representative. At any time during the trial and without giving reasons, a subject may decline to participate further. The subject will not suffer any disadvantage as a result.
- Progressive disease and dose limiting toxicity (DLT)
- Subject is lost to follow-up.
- Death.

Subjects **may be** withdrawn from the study for the following reasons:

- The subject is non-compliant with study drug, trial procedures, or both; including the use of anti-cancer therapy not prescribed by the study protocol.
- Pregnancy. Pregnancy will be reported as an SAE. (Note: subjects who have been withdrawn from treatment with study drug because of pregnancy should not undergo CT scans [with contrast]/MRI or bone scans while pregnant.)
- If, in the investigator's opinion, continuation of the trial would be harmful to the subject's well-being.
- The development of a second cancer.
- Development of an intercurrent illness or situation which would, in the judgment of the investigator, significantly affect assessments of clinical status and trial endpoints.

- Deterioration of ECOG performance status to 4.
- Use of illicit drugs or other substances that may, in the opinion of the investigator, have a reasonable chance of contributing to toxicity or otherwise skewing trial result.

Any subject removed from the trial will remain under medical supervision until discharge or transfer is medically acceptable.

In all cases, the reason for withdrawal must be recorded in the CRF and in the subject's medical records.

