- If exactly 1 of the 3 patients treated show DLT during the DLT assessment period, 3 additional patients are treated at the current dose level.
- If none of these additional 3 patients show DLT during the DLT assessment period, the dose level is escalated for the next cohort of 3 patients, and the process continues as above; otherwise, the prior dose level is defined as the MTD (unless only 3 patients have been treated at that level, in which case it is the tentative MTD).
- A tentative MTD becomes final when a total of 6 patients are treated with less than 2 showing DLT.
- If 2 of the first 3 patients have hematologic DLT, then next cohort will be dose level -1.

Study visits during the treatment period should occur at 4 weeks intervals (within a window of +/- 7 days). **Dosing delays** may be instituted under the following circumstances:

Disease progression:

The Investigator should delay cytotoxic chemotherapy, other systemic radioisotope, hemibody external radiotherapy or other investigational drug until the follow-up period. If such treatments have to be given during the treatment period, further study drug administrations must be discontinued. Patients with disease progression may continue other treatment at the Investigator's discretion.

Myelosuppression:

Treatment-related changes in hematology parameters may occur.

- Blood transfusion is acceptable between study drug administrations. Use of biologic response modifiers, such as G-CSF or GM-CSF, is allowed in the management of acute toxicity.
- If myeloid growth factors are required for the management of acute toxicity this event should be considered a DLT.

Gastrointestinal events:

Diarrhea should be treated as per local practice. A further dose of study medication should not be given before diarrhea is recovered to CTCAE v4.03 Grade 2 or baseline levels.

Nausea or vomiting should be treated as per local practice. A further dose of study medication should not be given before nausea or vomiting is recovered to CTCAE v.4.03 Grade 2 or baseline levels.

For any grade 3 hematologic toxicity for >14 days, study drug administrations must be discontinued (grade 4 events of anemia and neutropenia >7 days are dose-limiting).

Spinal Cord Compression:

If the patient experiences spinal cord compression during the treatment period, the patient should be treated for the event, and this will be considered disease progression.

Surgical Intervention:

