If surgery is required, the patient should continue with study treatment, if this is considered safe in the treating Investigator's opinion. The surgeon needs to be notified that the patient has been given radioactive drug, and needs to follow the guidelines for radioactive protection.

Non-pathological fractures:

For traumatic fractures in weight-bearing bones during treatment phase, the study drug administration should be delayed for 2-4 weeks from the time of fracture.

Pathological fractures:

Pathological fractures may occur as the result of either progressive disease or increased physical activity associated with significant pain palliation. Pathologic fractures are to be treated in a manner that attempts to maintain the best functional status and quality of life. Study treatment may continue as planned.

Any Other Toxicity: Local practice will apply.

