6.5 Prior and concomitant therapy-

During treatment, all concomitant medications (including start/stop dates and indication) must be recorded in the patient's medical record and case report form (DMI)

Permitted

- Treatment with non-conventional therapies (e.g., herbs [with the exception of St. John’s Wart], acupuncture) and vitamin/mineral supplements is acceptable provided that, in the opinion of the investigator, such treatment will not interfere with the trial endpoints.
- Subjects may receive standard of care for any underlying illness.
- In the event of neutropenia, anemia, or thrombocytopenia, subjects may receive appropriate supportive care (e.g., transfusion, biologic response

modifiers such as G-CSF or GM-CSF, prophylactic antibiotics, antifungals and/or antivirals, hematopoietic growth factors). This supportive care should not substitute a recommended dose modification.

- Blood transfusions and erythropoietin are allowed during the study period
- If surgery is required during study drug treatment, the surgeon needs to be notified that the patient has been treated with a radioactive product and adequate precautions for radioactive protection should be applied during the surgical procedure. The patient should continue with study treatment if considered safe in the treating Investigator's opinion.

7. Procedures and variables

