8.1 Analysis sets

Safety monitoring rule

- Should DLTs occur in more than two patients at any time during the dose expansion phase clinical personnel and study investigators will meet and assess the attribution, severity and nature of the DLTs. No additional patients will be accrued until the data is reviewed and a decision is made to continue at the current dose or to de-escalate the prior dose as the dose for the expansion phase. This review and decision will be documented in writing.

Monitoring of alkaline phosphatase

- Alkaline phosphatase, a biomarker associated with osteosarcoma metastases, will be determined monthly before administration of each dose of Ra-223 dichloride. The trend of improvement (or not) will be analyzed for a particular patient and number of patients in a cohort with improvement as a function of dose # will be analyzed.

Imaging

- Nuclear Medicine Studies will use commercially available ^{99m}Tc , ^{18}F Fluorodeoxyglucose and sodium ^{18}F Fluoride to image indicator lesions. The trend of improvement (or not) in ^{99m}Tc -MDP on SPECT CT, ^{18}F FDG-PET-CT SUV, or Na^{18}F SUV will be compared for study entry vs after dose #3 and study entry vs after dose #6 and after dose #3 vs after dose #6 will analyzed for a particular patient and number of patients in a cohort with improvement after dose #3 and dose #6 will be analyzed.
- Analysis of lung metastases. Up to 3 measurable (1 cm or larger) indicator lesions seen on chest CT may be described at study entry and compared after dose #3 and dose #6. RECIST criteria (>20% increase in size) will be used as criteria for progression. Any change <20% or if size is <1 cm will not be used for “off study” progression criteria.
- RECIST progression will determine progressive disease regardless of other imaging.

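### Surgery and some other anti-tumour treatments can be given on study without a mandatory stop, and no analysis rule keeps their effects out of the Ra-223 improvement counts

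*Combined protocol and SAP*

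**What the plan says.** **Entry.** Section 5.1.2 excludes "Concurrent anti-cancer therapy (chemotherapy, radiation therapy, surgery, immunotherapy, biologic therapy, or tumor embolization").

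**On study, mandatory stop.** Under Dose Modification and Escalation (following section 6.2.9), the Disease progression paragraph says "The Investigator should delay cytotoxic chemotherapy, other systemic radioisotope, hemibody external radiotherapy or other investigational drug until the follow-up period". It continues: "If such treatments have to be given during the treatment period, further study drug administrations must be discontinued". The stop therefore attaches to those four classes.

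**On study, surgery.** The Surgical Intervention paragraph says "If surgery is required, the patient should continue with study treatment, if this is considered safe in the treating" investigator's opinion. Section 6.5 repeats this in its list of permitted items: "The patient should continue with study treatment if considered safe in the treating Investigator's opinion". Neither place limits the permission to sites other than the indicator lesion.

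**Withdrawal.** Section 5.2.1 puts progressive disease among the mandatory reasons. Among the optional reasons it puts non-compliance, "including the use of anti-cancer therapy not prescribed by the study protocol", and also situations that the investigator judges would materially affect endpoint assessment.

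**Analysis.** Section 7.2 bases efficacy on trends in indicator-lesion uptake, labelled exploratory, and on ALP before treatment, after three doses and after six. For imaging, section 8.1 states that the "number of patients in a cohort with improvement after dose #3 and dose #6 will be analyzed". It counts ALP improvement per cohort in the same way and compares the size of up to three lung lesions at the same times. Section 8.3 only refers back to this text.

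**The concern.** The secondary objective (section 2.2) is the response of indicator lesions to Ra-223, and the synopsis plans a comparison of uptake between dose groups. Both need the change to be attributable to the study drug. Section 1.1 leaves combination with surgery or external beam radiotherapy to future work, so the question here is Ra-223 alone.

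If an indicator lesion is resected, its uptake and size are no longer a measure of drug effect, and ALP may fall because bone-forming tumour has been removed. Irradiation or embolization could act in the same direction, though that is an assumption. The trial has no control group. If local treatment were uneven across dose levels, the dose comparison would be distorted as well.

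Such treatment is foreseeable. Section 1.2 describes surgery as critical in relapsed disease, and the protocol provides for on-study surgery in two places.

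**Working it through.** The plan gives no figure for this point, so the check is a comparison of text followed by simple arithmetic.

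**Step 1. Which treatments are excluded at entry, and which force a stop on study?**

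| Treatment | Entry (5.1.2) | Mandatory stop (Disease progression paragraph) | Otherwise |
|---|---|---|---|
| Cytotoxic chemotherapy | excluded | yes | – |
| Another systemic radioisotope | not named separately | yes | – |
| Hemibody radiotherapy | excluded as radiation | yes | – |
| Investigational immunotherapy or biologic | excluded | yes, as another investigational drug | – |
| Non-investigational immunotherapy or biologic | excluded | not listed | optional withdrawal (5.2.1) |
| Focal radiotherapy | excluded | not listed | optional withdrawal (5.2.1) |
| Embolization | excluded | not listed | optional withdrawal (5.2.1) |
| Surgery | excluded | not listed | dosing continues if judged safe |

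The last four rows are the gap. It is clearest for surgery, because surgery that the protocol permits is not non-compliance.

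**Step 2. Does the analysis close the gap?** Sections 7.2 and 8.1 fix the comparison times and count improved patients. Section 8.1 is headed Analysis sets but defines no efficacy set, no evaluability condition and no handling of a treated lesion. Section 8.3 adds nothing. The gap stays open.

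**Step 3. How much does one patient matter?** Let n be the cohort size, with one affected patient and x improved among the other n − 1.

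- Counted as improved: (x + 1)/n
- Kept as not improved: x/n
- Removed from the denominator: x/(n − 1)

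Counted as improved minus kept as not improved is always 1/n:

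- n = 3 (escalation cohort): 1/3 = 33.3 points
- n = 6 (expansion cohort): 1/6 = 16.7 points
- n = 8 (100 kBq/kg row of Table 1): 1/8 = 12.5 points
- n = 20 (maximum total): 1/20 = 5 points

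Counted as improved minus removed is (x + 1)/n − x/(n − 1) = (n − 1 − x)/[n(n − 1)]. This runs from 1/n when x = 0 down to 0 when x = n − 1.

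**Step 4. Does the choice of denominator matter?** Take, for illustration, n = 3 and x = 1. Counted as improved gives 2/3 = 67%, removed gives 1/2 = 50%, and kept as not improved gives 1/3 = 33%. With n = 6 and x = 2 the three figures are 3/6 = 50%, 2/5 = 40% and 2/6 = 33%. A rule that only calls such values not evaluable, without saying what happens to the denominator, would leave this choice open.

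**The case against.** Several points on the other side have force.

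- **Withdrawal is available.** Section 5.2.1 allows it for anti-cancer therapy outside the protocol and for situations that affect endpoints. A treated indicator lesion fits the second ground. This stands as mitigation, but both grounds are optional and neither says how data already collected, or collected later, are counted.
- **Progression closes the commonest route.** Section 5.2.1 requires withdrawal for progressive disease, and section 6.2.2 requires indicator lesions to be no worse than stable before dose 4. Patients treated locally because of declared progression should leave the trial. This stands, although the Disease progression paragraph blurs it by leaving other treatment to the investigator. What remains is treatment without declared progression.
- **The passages can be read together.** Required surgery, discussed beside fractures, may mean surgery that is not anti-cancer surgery. Concurrent in section 5.1.2 may also reach into the treatment period. A reader might infer a flat contradiction, but the text supports only ambiguity or inconsistency.
- **Section 8.1 does not order treated lesions to be counted.** This is correct. It gives no rule, so counting them is possible but not prescribed. Complete loss of uptake is one possible coding of a resected lesion.
- **The treatment would be noticed.** CT or MRI of all disease sites is required at baseline and restaging, and trends are examined for each patient. In a trial of at most 20 patients a resection would normally be seen. Seeing it does not settle how it is classified, and an ALP value carries no such flag.
- **The stakes are limited.** The imaging trends are labelled exploratory, although ALP is not, and neither measure enters the DLT or MTD rules. This stands.

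**Conclusion.** The point holds in a limited form. The protocol lets a patient continue Ra-223 after surgery without excluding surgery on the indicator lesion. It makes withdrawal only optional for focal radiotherapy, embolization and non-investigational immunotherapy or biologic therapy when progression has not been declared. Because sections 7.2 and 8.1 set no condition on intervening treatment, a change caused by such treatment can enter the improvement counts.

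One patient shifts the proportion by 33 points in a cohort of 3, 17 in a cohort of 6 and 12.5 in a group of 8, measured against keeping that patient as not improved. The shift is equal or smaller when measured against removal. The direction is clear for resection and assumed for the other treatments. The documents give no frequency, so no expected bias can be stated.

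A reader might infer that these treatments never stop study drug, or that the dose recommendation is at risk. The documents support neither. Withdrawal is possible under section 5.2.1 and required at progression, investigational agents already force a stop, and the DLT and MTD rules use toxicity only. The correction is still worth making, because these counts are the trial's planned evidence of response and the change is small.

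**What to change.** 1. **Add an evaluability rule to section 8.1.**
   - An indicator lesion that is resected, embolized or irradiated on study is not evaluable for uptake or size change from that date.
   - ALP and uptake values taken after any anti-tumour treatment other than study drug, including surgery that the protocol permits, are not evaluable for improvement.
   - Earlier values are kept.
   - Affected patients are listed with the treatment and its date.
   - Per-cohort counts are shown twice: with affected patients removed from the denominator, and with them kept as not improved.
2. **Reconcile the treatment passages.** Section 5.1.2, section 5.2.1, the Disease progression and Surgical Intervention paragraphs, and section 6.5 are ambiguous or inconsistent on which concurrent treatments are compatible with study treatment. The sponsor must decide what applies. No clinical rule is proposed here.

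The cost is wording in the protocol and its statistical section. A few late values are lost, and the response counts may look slightly less favourable. Sample size, dose escalation and DLT assessment do not change.

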6.2.1 Radium-223 dichloride

6.2.2 Treatments to be administered

Ra-223 dichloride will be administered as a slow bolus IV injection at intervals of every 4 weeks for up to 6 cycles.

- Dose (50, 75, or 100 kBq/kg) will be assigned in cohorts of 3 after study registration in CORE.
- Dose #1 should be given within 30 days of study registration
- At least 3 patients will be required to successfully complete 6 weeks of therapy before advancing to the next cohort.
- Patients will receive the same Ra-223-dichloride dose as dose #1 for all subsequent doses.
- Monthly dosing (q 4 weeks +/- 6 days) as slow iv bolus for up to a total of 6 doses
- Monthly doses will be delayed, but no more than 2 weeks from scheduled dose for any grade 3 hematologic toxicity.

Criteria for subsequent doses (i.e. doses 2-6):

- Hematologic Toxicity (if present): Hb, ANC, and platelets- resolved to grade 2 or less within 6 weeks of prior dose. Since lymphopenia may be chronic, this will not be a criteria for subsequent doses
- All toxicities must be resolved to grade 2 or less in order to begin subsequent cycles
- Performance status ECOG 0 to 2
- Alkaline phosphatase stable or improving at the discretion of the treating physician
- Not on oxygen
- Not pregnant
- After dose #3 and before dose #4: stable disease or better in indicator lesions as determined by quantitative nuclear medicine imaging (^{18}F FDG PET-CT, quantitative $^{99\text{m}}\text{Tc}$ -MDP SPECT/CT, or Na^{18}F PET/CT) or RECIST criteria on anatomic imaging (note: often osteosarcoma "indeterminate" lesions 1-9 mm remain stable or have minimal change depending on chest CT technique).
- Anatomic imaging (CT or MRI) of all sites of disease along with chest CT at baseline and restaging for all patients will be done to allow for assessment of RECIST progression.
- RECIST progression will determine progressive disease regardless of other imaging.

For the Phase I aspect of the protocol, prior to advancing/changing dose levels, a cohort summary must be completed and submitted to the Clinical Research Monitor in the IND Office.

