beforehand and given suitable personal protection equipment (i.e. universal blood and body fluid precautions - especially when handling ashes containing potentially radioactive bone fragments. Calculations and the rationale for radiation dose estimates are available upon request (see investigators Brochure).

Definition of Dose-Limiting Toxicities (DLTs):

Toxicities will be graded in severity according to the guidelines outlined in the NCI Common Terminology Criteria for Adverse Events (CTCAE) version 4.0 (publish date 28-May-2009). Dose-limiting toxicities include all adverse experiences that are related to study medication, and clearly not related to disease progression or intercurrent illness.

Based on prior experience with other bone seeking radiopharmaceuticals and Ra-223 dichloride in prostate cancer patients, the expected dose limiting toxicity (DLT) will be hematologic. Lymphopenia is common in patients with bone metastases and will be monitored, but not considered a DLT in this protocol. Any grade 4 anemia, any grade 4 neutropenia for >7 days or grade 4 neutropenia with fever (a single temperature greater than 38.3°C or a sustained temperature of $\geq 38^\circ\text{C}$ for more than one hour) and grade 3 or 4 thrombocytopenia with clinically significant bleeding will be dose limiting. Grade 3 non-hematologic toxicities except for nausea, emesis or diarrhea that are controlled with maximal medical management within 72 hours will be considered dose-limiting. DLTs will only be monitored during the first 6 weeks of treatment. Ongoing toxicity that causes a delay of more than 2 weeks in starting the next cycle will also be dose-limiting if it occurs during the first cycle.

Dose Modification and Escalation

Every effort should be made to administer the full dosing regimen of Ra-223 dichloride. Adjustment of dose level is not permitted.

- A minimum of 3 patients initially will be enrolled at the first dose level.
- If at least 2 patients are observed to have a dose-limiting toxicity (DLT), the MTD will have been exceeded and no further patients will be enrolled at this dose level or at any higher dose level. The prior dose level is defined as the MTD (unless only 3 patients have been treated at that level, in which case it is the tentative MTD).
- If 0 of the 3 patients are observed to have DLT during the DLT assessment period, the dose level is escalated one step for the next cohort of 3 patients, and the process continues as above.

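### The mandatory stop for grade 3 hematologic toxicity beyond 14 days has no lymphopenia exception, although the protocol elsewhere means to tolerate lymphopenia

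*Combined protocol and SAP*

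**What the plan says.** The stop rule is in section 6.2.9, under Dose Modification and Escalation, and is printed at the end of the Gastrointestinal events paragraph: "For any grade 3 hematologic toxicity for >14 days, study drug administrations must be discontinued". A parenthesis follows about grade 4 anemia and neutropenia. It does not mention lymphopenia.

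Two sentences elsewhere set lymphopenia apart:

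- Section 6.2.2, within the hematologic toxicity criterion for doses 2 to 6: "Since lymphopenia may be chronic, this will not be a criteria for subsequent doses".
- The DLT definition in section 6.2.9: "Lymphopenia is common in patients with bone metastases and will be monitored, but not considered a DLT in this protocol".

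Two other bullets in section 6.2.2 act on toxicity without repeating the exception:

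- "Monthly doses will be delayed, but no more than 2 weeks from scheduled dose for any grade 3 hematologic toxicity"
- "All toxicities must be resolved to grade 2 or less in order to begin subsequent cycles"

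For hemoglobin, neutrophils and platelets, section 6.2.2 asks that toxicity be "resolved to grade 2 or less within 6 weeks of prior dose". The dose level may not be changed for any patient, and section 6.2.9 adds: "Every effort should be made to administer the full dosing regimen of Ra-223 dichloride".

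**The concern.** The protocol treats lymphopenia as a hematologic toxicity, expects it to be common and possibly chronic, and decides that it should neither hold back the next dose nor count as a DLT. The stop rule then covers every hematologic toxicity at grade 3, sets a limit of 14 days and leaves no discretion. Anyone applying that sentence alone would permanently stop a patient whom the rest of the plan means to keep on treatment.

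Dose reduction is not allowed, so the only outcomes are to continue or to stop. The data that would trigger the rule are collected routinely: Table 4 requires a blood count with differential, every two weeks in the first two cycles. At stake are doses delivered and the secondary alkaline phosphatase and imaging comparisons after doses 3 and 6.

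**Working it through.** The plan gives no figure to reproduce here. The check compares the rules and counts days.

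**1. Is lymphopenia inside the stop rule?** Section 6.2.2 handles it within its hematologic toxicity bullet, so the protocol itself classes it as hematologic. The stop rule covers any hematologic toxicity. No sentence in the document exempts lymphopenia from it.

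**2. How each rule treats persistent grade 3 lymphopenia**

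| Rule | Place | Literal result |
|---|---|---|
| Redosing waiver | 6.2.2 | No bar to the next dose, no time limit |
| DLT definition | 6.2.9 | Not a DLT |
| Grade 3 delay bullet | 6.2.2 | Delay, at most 2 weeks |
| All-toxicities bullet | 6.2.2 | No next cycle until grade 2 or less |
| Stop rule | 6.2.9 | Permanent stop after 14 days |

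The first two rows say tolerate; the last three say delay, hold or stop.

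**3. Does the result depend on how the 14 days are counted?** Take the dose as day 0 and the next scheduled dose as day 28. The latest permitted dose is day 28 + 14 = 42, which equals the 6-week limit in section 6.2.2. Assume grade 3 lymphopenia that starts on day 14 and does not resolve.

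- Days at grade 3: on day 29 the duration is 29 − 14 = 15 days, more than 14. Stop.
- Days past the scheduled dose: on day 43 the count is 43 − 28 = 15 days, more than 14. Stop. If this clock is taken to mean days of actual delay, the result also needs the delay bullet to be read literally; if the waiver lets dose 2 go ahead on day 28, no delay accrues.

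So, with every rule read literally, persistent lymphopenia ends treatment under either count.

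**4. What a stopped patient loses.** Doses lost = 6 − doses already given.

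- After dose 1: 6 − 1 = 5 doses, and the comparisons after dose 3 and after dose 6.
- After dose 2: 6 − 2 = 4 doses, and both comparisons.
- After dose 3: 6 − 3 = 3 doses, and the comparison after dose 6.
- After dose 4 or 5: 2 or 1 doses, and the comparison after dose 6.

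The loss of 5 doses is possible under the days-at-grade-3 count when onset is on day 13 or earlier, because 28 − 13 = 15 days have then passed when dose 2 falls due.

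**5. The clock for the other cell lines.** Assume grade 3 thrombocytopenia without bleeding from day 14 to day 35. Counted at grade 3 it lasts 35 − 14 = 21 days, so the patient stops. Counted from the scheduled dose it lasts 35 − 28 = 7 days, so the patient continues, having recovered by day 42. The two counts can lead to different decisions, so the sentence should say which applies.

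**The case against.** The best reply is that the specific sentence governs the general one. The authors stated twice that lymphopenia is to be tolerated, and the hematologic redosing criterion names only hemoglobin, neutrophils and platelets. A sensible investigator would carry the exception over. This has force for the two bullets in section 6.2.2, which stand in the same section as the waiver. It has less force for the stop rule, which stands in another section, under a gastrointestinal heading, with no cross-reference and in mandatory terms.

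The reply on the clock is also sound. A toxicity lasting more than 14 days most naturally means days at that grade. The DLT definition uses the same form for neutropenia, and where the protocol means delay it names the scheduled dose or the next cycle. On that reading the stop rule and the redosing criterion for hemoglobin, neutrophils and platelets can both be obeyed: meeting the criterion is necessary for redosing, and the stop rule adds a further condition. A reader might infer that these two rules contradict each other; they do not.

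A reader might also infer that lymphopenia could become a DLT through the first-cycle clause, "Ongoing toxicity that causes a delay of more than 2 weeks in starting the next cycle will also be dose-limiting", and so expand a cohort or lower the MTD. The documents do not support this. The same DLT definition expressly excludes lymphopenia, and because section 6.2.2 removes it from the redosing criteria, it should cause no delay.

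**Conclusion.** The point holds for the missing exception. As written, the stop rule and the grade 3 delay bullet conflict with the protocol's own treatment of lymphopenia, and a literal reader would stop a patient whom the plan intends to continue. The size per affected patient is up to 5 of 6 doses and one or both of the later alkaline phosphatase and imaging comparisons, which are secondary, with the scan trends described as exploratory in section 7.2.

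How many patients this would affect cannot be said, since the documents give no rate of grade 3 lymphopenia beyond 14 days. No sample size, error rate or DLT count changes. The conclusion concerns counts that start or worsen on treatment, and it assumes the stop rule is applied as worded. The clock is a lesser matter of clarity.

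**What to change.** In one amendment:

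- Reword the stop rule to cover *any grade 3 anemia, neutropenia or thrombocytopenia (not lymphopenia)* lasting more than 14 days, and move it from the Gastrointestinal events paragraph to Myelosuppression.
- Add *other than lymphopenia* to two bullets in section 6.2.2: the grade 3 delay bullet and the one requiring all toxicities to resolve to grade 2 or less.
- As a minor clarification, state whether the 14 days are days at grade 3 (the more natural reading) or days past the scheduled dose.

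The cost is a few words in three sentences, one sentence moved and one clarification. The stop for anemia, neutropenia and thrombocytopenia is not loosened. The downside is that patients with prolonged grade 3 lymphopenia keep receiving drug. Section 6.2.2 and the DLT definition already intend this, and section 5.2.1 lets the investigator withdraw a patient for whom continuing would be harmful.
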